2.6.	Lens Insertion	The Investigator or the subject inserts the study lenses. Record the time of lens insertion. Check for lens damage under the slit lamp before proceeding with lens settling. Replace damaged lenses if applicable.	
2.7.	Lens Settling	Allow the study lenses to settle for a minimum of 15 minutes.	
2.8.	Pupillometry	Measure the right eye pupil diameter during distance fixation (3 measures) using NeurOptics Pupillometer. EDC: record pupil diameters in mm (0.1 mm increments)	
2.9.	Distance ETDRS LogMAR Visual Acuity	Perform binocular (OU) distance ETDRS logMAR visual acuity test at a 4-meter distance under the following conditions with the study lenses on. The charts will be rotated during testing to reduce memorization. 1. Bright illumination (~500 lux) A. High contrast (90%) chart B. Low contrast (10%) chart 2. Dim illumination (~1 lux) A. High contrast (90%) chart	
2.10.	Contrast Sensitivity Bright Illumination	Perform binocular (OU) contrast sensitivity test under the following conditions with the study lenses on. The Pelli Robson charts will be rotated to reduce memorization. 1. Bright illumination (~500 lux) A. Pelli-Robson chart at 3 meters EDC: record log contrast sensitivity	

Visit 2: Laboratory measures of vision performance			
Step	Procedure	Details	
2.11.	Contrast Sensitivity Dim Illumination	
Perform binocular (OU) contrast sensitivity test under the following conditions with the study lenses on. The Pelli Robson charts will be rotated to reduce memorization.
 
 1. Dim illumination (< ~1 lux) 
 A. Mesotest II instrument B. With glare and without glare C. 4 contrast levels + 5 Landolt C targets per contrast level 
EDC: record the total targets correctly identified with glare and without glare
	
2.12.	Lens Removal	The study lenses will be removed and discarded. A fresh pair of lenses will be used for each trial.	
2.13.	Vison and lens assessments	Repeat 2.5 to 2.12 for the other two treatment conditions	

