6.1. Definition

Binocular visual performance:

The following measurements will be used to assess the performance of the test and control products in a controlled laboratory setting which simulate a wide range of visual conditions encountered while driving.

1. High luminance (~500 lux) high contrast (90%) LogMAR distance visual acuity

- 2. High luminance (~500 lux) low contrast (10%) LogMAR distance visual acuity
- 3. Low luminance (~1 lux) high contrast (90%) LogMAR distance visual acuity
- 4. High luminance (~500 lux) contrast threshold (Pelli-Robson chart)
- 5. Low luminance (~1 lux) contrast threshold (Mesotest II instrument by Oculus, Germany)

The order of the vision tests will be randomized for each condition. The ETDRS logMAR chart will be used, which is scored on a letter by letter basis (-0.02 log units per letter correctly identified). A number of different EDTRS charts will be used to reduce potential learning effects. Letter contrast sensitivity will also be determined binocularly using the Pelli-Robson chart, scored on a letter by letter basis (0.05 log units per each letter correctly identified). The ETDRS logMAR chart and the Pelli-Robson contrast sensitivity chart are validated techniques routinely used in research to accurately quantify visual performance. Room illuminance will be controlled using dimmer switches and quantified using a lux meter.

There will be two secondary endpoints considered from binocular visual performance evaluation:

- Low luminance ~1 lux) high contrast (90%) distance visual acuity
- Low luminance (~1 lux) contrast threshold

During low luminance contrast threshold evaluation, five Landolt C targets in random orientation will be presented for each of the four contrast levels 95%, 80%, 63% and 50%. Participants will be asked to correctly identify the orientation of the Landolt C. The number of correct response will be recorded for each contrast level. This entire test will be done with and without the presence of a glare source.

Sign recognition (percentage)

Participants will be instructed to report the identity of a percentage of the standard road signs (typically about 42 signs dependent on the route travelled) containing about 65 items of information as they drive around the circuit. We will also measure the recognition distance using the in-vehicle measurement system for one specific road sign while the participant is driving.

Hazard avoidance:

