6.2. Secondary Analysis Methods

Binocular distance visual acuity (LogMAR)

Binocular low luminance high contrast distance visual acuity will be analyzed using a linear mixed model to test for the difference between Test and Control 1. Sequence of lens wear, period, lens type, first order carryover effect will be included in the model as fixed effects. An appropriate covariance structure will be chosen to model the residual errors between measurements within the same subject across periods. Covariance structures considered will be:

- Compound Symmetry (CS)
- Heterogeneous Compound Symmetry (CSH)
- Unstructured (UN)
- Ante-dependence (ANTE(1))

For ANTE(1) structure, subject will be included in the model as random effects. The covariance structure that returns the lowest AICC will be selected as the structure that best fit the data.

The null and alternative hypotheses for non-inferiority of Test lens relative to Control 1 are as follows:

$$H_0: \mu_T - \mu_C \ge 0.1 H_A: \mu_T - \mu_C < 0.1,$$

where $\mu_T - \mu_C$ is the mean difference between Test lens and Control 1 lens. Non-inferiority of the Test lens relative to the Control 1 lens will be concluded if the upper limit of the 95% confidence interval of the LSM difference between Test and Control 1 is less than 0.1.

Low luminance contrast threshold (%)

Low luminance contrast threshold will be analyzed using a generalized linear mixed model with a binomial distribution and the logit and the link function. Sequence, period, lens type, first order carry-over, contrast level and the interaction contrast level by lens type will be included as fixed effects and subject as random effect. An unstructured covariance matrix (UN) will be used to model the correlation between measurements from the same subject and period across contrast level. If convergence problems are encountered with the unstructured covariance matrix, a model with compound symmetry covariance matrix (CS) will be considered

The null and alternative hypotheses for no-difference between Test and Control 1 are as follows:

$$H_0: OR = 1 H_A: OR \neq 1,$$

where OR is the odds ratio of the number of correctly identified orientation of the Landolt C. No statistical difference between Test lens and Control 1 lens will be concluded if 1 falls within the 95% confidence interval of the LSM ratio, OR, of Test Over Control 1.

Sign Recognition and Hazard Avoidance (%)

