CLASS tseqpg2 aperiod trta carry1a subjid parcat6 sexn ; MODEL aval/n= age sexn tseqpg2 aperiod trta|parcat6 carry1a / S DIST=BINOMIAL LINK=LOGIT; RANDOM INTERCEPT / SUBJECT=subjid; RANDOM parcat6 / RESIDUAL SUBJECT=aperiod(subjid) TYPE= covariance_matrix; ESTIMATE "Test vs Control1" lens -1 0 1, *secondary analysis; "Test vs Control2" lens 0 -1 1 / CL ILINK EXP; *other analysis;

RUN;

Where ads: Analysis data set n: number of targets subjid: subject identification sexn: Gender tseqpg2: Lens wear sequence (6 levels) aperiod: Study Period (3 levels) trta: Study lens type (Test, Control1, Control2) parcat6: Contrast level (4 levels) carry1a: First order carryover effect covariance_matrix: Compound Symmetry (CS) and Unstructured (UN)

Sign Recognition and Hazard Avoidance

PROC GLIMMIX DATA= ads;

CLASS driveseq asper trta carry1a parcat5 sexn; MODEL aval= age sexn driveseq asper|parcat5 trta|parcat5 carry1a / DDFM=KR2 S DIST=BETA LINK=LOGIT; RANDOM INTERCEPT / SUBJECT=subjid; RANDOM asper / RESIDUAL SUBJECT= parcat5 (subjid) TYPE=covariance_matrix; **Secondary analysis; ESTIMATE "Night: Test vs Control1" trta -1 0 1 trta*parcat5 0 -1 0 0 0 1 / CL ILINK EXP; **Other Analysis; ESTIMATE "Day: Test vs Control1" trta -1 0 1 trta*parcat5 -1 0 0 0 1 0, "Day: Test vs Control2" trta 0 -1 1 trta*parcat5 0 0 -1 0 1 0, "Night: Test vs Control2" trta 0 -1 1 trta*parcat5 0 0 0 -1 0 1 / ADJUST=bonferroni CL ILINK EXP ;

RUN;

Where ads: Analysis dataset subjid: subject identification sexn: Gender driveseq: Lens wear sequence (6 levels) asper: Study Period (3 levels) trta: Study lens type (Test, Control1, Control2) parcat5: Driving time (day or night) carry1a: First order carryover effect covariance matrix: Compound Symmetry (CS) and Unstructured (UN)

Pedestrian Distance Recognition and Road Sign Recognition

PROC GLIMMIX DATA= ads;

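### Visit 2 step 2.11 has the site enter only total targets correct, while the endpoint definition and the SAP model need a count at each of four contrast levels

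*Protocol*

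**What the plan says.** Protocol 7.2, Visit 2, step 2.11 describes the Mesotest II layout as "4 contrast levels + 5 Landolt C targets per contrast level", run with and without glare. The same step then states what is to be entered: "EDC: record the total targets correctly identified with glare and without glare". Glare is the only split it names.

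The endpoint definition differs. SAP 6.1 says: "The number of correct response will be recorded for each contrast level". Protocol 2.2.2 has the same sentence. Both list the four levels as 95%, 80%, 63% and 50%, with five targets at each.

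The analysis is built on those per-level counts. In SAP 6.2, "contrast level and the interaction contrast level by lens type will be included as fixed effects", and an unstructured matrix models the "correlation between measurements from the same subject and period across contrast level", with compound symmetry as the fallback if the model does not converge. Appendix A codes this as "MODEL aval/n= age sexn tseqpg2 aperiod trta|parcat6 carry1a" and defines the contrast factor as "parcat6: Contrast level (4 levels" in the code key. Protocol 14.6 had a Poisson model with the same contrast-level terms.

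The hypothesis concerned is secondary hypothesis 2 (Protocol 2.3.2, SAP 1.4.2), Test against Control 1 without glare.

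**The concern.** The step that tells the site what to enter asks for less than the endpoint definition and the model require. The SAP does not resolve the conflict. By SAP 1.1 it takes precedence over Protocol section 14 only, so step 2.11 stands. Protocol 15.1 says the eCRFs are designed around the procedures of each visit, which makes step 2.11 a natural source for the form.

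Totals can always be built from per-level counts, but not the other way round. A hypothetical score of 5, 5, 3, 1 across the four levels and one of 4, 4, 3, 3 both sum to 14, so the total does not show how performance falls with contrast. If only totals were entered and no other record kept, the planned analysis of one of the six secondary hypotheses could not be carried out.

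**Working it through.** The plan states no figure on this point, so there is none to reproduce. The check compares what the model needs with what step 2.11 supplies.

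**Inputs.** Four contrast levels, five targets per level and two glare conditions (Protocol 2.2.2 and step 2.11); three lens conditions and six Williams sequences (Protocol 5.1, SAP 1.6); 24 completers (Protocol 14.2, SAP 1.5); model terms from SAP 6.2 and Appendix A.

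**Values per lens and subject.**
- Targets per glare condition: 4 × 5 = 20.
- Counts under the endpoint definition: 4 for the without-glare condition; 4 × 2 = 8 over both.
- Values under step 2.11 read literally: 1 for the without-glare condition; 2 over both.

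**Records for the without-glare analysis, 24 completers.**
- Per-level capture: 24 × 3 × 4 = 288 records, each out of 5 targets.
- Total only: 24 × 3 = 72 records, each out of 20 targets.

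**Estimable fixed effects.** The design matrix was built with sequence, period, lens, first-order carry-over, contrast level and contrast level by lens. Age and sex were left out because they do not bear on the question.

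| Term | df, per-level counts | df, totals only |
|---|---|---|
| Intercept | 1 | 1 |
| Sequence (6 levels) | 5 | 5 |
| Period (3) | 2 | 2 |
| Lens (3) | 2 | 2 |
| Carry-over (none in period 1, then one of three lenses) | 2 | 2 |
| Contrast level (4) | 3 | not estimable |
| Contrast level × lens | 3 × 2 = 6 | not estimable |
| **Rank** | **21** | **12** |

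Carry-over adds 2 df and not 3 because its no-carry-over category coincides with period 1. The computed ranks were 21 and 12, a loss of 21 − 12 = 9 df.

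**Covariance across levels.** The unstructured 4 × 4 matrix has 4 × 5 / 2 = 10 parameters and needs four records per subject and period. With one total per subject and period there is no across-level correlation to estimate, whether unstructured or compound symmetric. The SAP's stated fallback therefore does not help.

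**What remains with totals only.** A binomial model with 20 trials per record, sequence, period, lens and carry-over, and a random subject effect could be set up. It gives an overall Test to Control 1 odds ratio, but it is not the model in SAP 6.2.

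**The case against.** The strongest reply is that the plan already requires per-level recording. Protocol 2.2.2 is part of the same protocol and binds the site too, and SAP 6.1 repeats it. On this view step 2.11 is an abbreviated line that comes directly after the list of levels and targets, and its total may mean the total at each level. This shows the intent, and it is why the point is an inconsistency and not a missing requirement. It does not remove the conflict: the step names glare as the only split, and its natural reading is one total per glare condition.

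A reader might infer that the per-level data will be lost for good. The documents do not support that. The eCRF is not included. Protocol 15.2 allows the subject record to be an external record, and Protocol 15.1 provides for equipment data held outside EDC. Neither section names this test, so retention is not shown either.

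A reader might also infer that the endpoint could not be analysed at all. That goes too far. Appendix A estimates a single overall lens contrast for Test against Control 1, and the reduced model on the total could still address that comparison. SAP 11.3 would require the change to be documented and justified.

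Nor do the documents suggest that totals were a deliberate choice. Protocol 2.2.2, Protocol 14.6, SAP 6.1, SAP 6.2 and Appendix A all assume per-level counts.

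Finally, the hypothesis is without glare only, as is the matching Control 2 comparison in SAP 7. The shortfall that matters for inference is therefore 1 value against 4, not 2 against 8.

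**Conclusion.** The point holds as an internal inconsistency; step 2.11 is wrong as written. Its data-entry instruction conflicts with the protocol's own endpoint definition, with SAP 6.1, and with the model in SAP 6.2 and Appendix A.

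The consequence is conditional. It rests on two assumptions: that the eCRF follows the literal wording of step 2.11, and that no per-level record is kept elsewhere. Under both, the pre-specified model for secondary hypothesis 2 cannot be fitted. What is lost is the contrast-level terms (9 df) and the across-level covariance, for every subject and all three lens conditions. The overall lens comparison would survive only in a reduced, unplanned form.

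The primary endpoint, sample size and power do not depend on this. It should be corrected because the remedy is small and counts not recorded at the visit cannot be rebuilt from totals.

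**What to change.** Reword the data-entry line of step 2.11 to: *EDC: record the number correct out of 5 at each contrast level (95%, 80%, 63%, 50%), separately with and without glare.* Check that the eCRF has matching fields. Totals, if wanted, can be derived from these.

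The cost is 8 − 2 = 6 more numeric fields per lens, or 6 × 3 = 18 per subject over the three lens conditions. The test itself does not change, and the analysis text in SAP 6.2 and Appendix A needs no change on this point.

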7.3. Unscheduled Visits

If, during the investigation, a subject requires an unscheduled visit to the clinical site, the following information will be collected at a minimum:

- Chief complaint prompting the visit. If the reason is an adverse event, the applicable eCRF for the adverse event must be completed and subject record completed as appropriate
- Date and time of the visit and all procedures completed at the unscheduled visit
- Review of adverse event and concomitant medications
- Documentation of any test article dispensed or collected from the subject, if applicable
- Slit lamp findings (using the Slit Lamp Classification Scale)

If the Investigator withdraws a subject from the study, the final study visit case report forms must be completed indicating the reason(s) why the subject was withdrawn. The subject record must be completed documenting the date and primary reason for withdrawal and the study CRA notified.

Any ocular and non-ocular Adverse Events that are ongoing at the time of the study visit will be followed by the Investigator, within licensure, until they have resolved, returned to pre-treatment status, stabilized, or been satisfactorily explained. If further treatment i.e., beyond licensure is required, the subject will be referred to the appropriate health care provider.

The following information will be collected during an unscheduled visit.

Step	Procedure	Details	
U.1	Chief Complaints	Record the subject's chief complaints for reasons for the unscheduled visit	
U.2	Change of Medical History and Concomitant Medications	Questions regarding the change of subjects' medical history and concomitant medications.	

Step	Procedure	Details	
U.3	Entrance VA	Record the entrance distance visual acuity (OD, OS and OU) to the nearest letter.	
U.4	Subjective Sphero-cylindrical Refraction	Perform bare-eye subjective spherocylindrical refraction with a phoropter (adopt the maximum plus to maximum visual acuity (MPMVA) approach and use the duo-chrome test for binocular balancing) and record the best corrected distance visual acuity to the nearest letter (OD, OS, OU).	
U.5	Slit Lamp Biomicroscopy	FDA Slit Lamp Classification Scale will be used to grade the findings. If no slit lamp finding is noted on the EDC form it is considered as a zero "0" grade for all observations listed. After the slit lamp examination, at the discretion of the Investigator, rinse the subject's eyes thoroughly with preservative-free saline.	
U.6	Exit Visual Acuity	Record the subject's exit distance visual acuity (OD, OS and OU) to the nearest letter with the subjects wearing the study provided spectacle glasses.	

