3.2. Inclusion Criteria

Potential subjects must satisfy all of the following criteria to be enrolled in the study:

1. The subject must read, understand, and sign the STATEMENT OF INFORMED CONSENT and receive a fully executed copy of the form
2. Appear able and willing to adhere to the instructions set forth in this clinical protocol
3. Between 20 and 49 (inclusive) years of age at the time of screening
4. Presbyopic subjects must be habitual wearers of distance vision correction in both eyes.

5. The subject's vertex corrected spherical equivalent distance refraction must be in the range of -1.00 through -6.00 D (inclusive) in each eye
6. The subject's refractive cylinder must be ≤ 1.00 D in each eye.
7. Have spherocylindrical best corrected visual acuity of 20/20 or better in each eye
8. Be a current soft contact lens wearer in both eyes, defined as at least 5 days per week and 6 hours per day averaged over the past 30 days.
9. Hold a current Open driver's license
10. Be a regular driver (at least once per week)
11. Have at least one year of driving experience

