6. STUDY INTERVENTION

6.1. Identity of Test Articles

The following contact lenses will be used in this study:

Table 2: Test Articles

	Test	Control 1	Control 2
Name	Senofilcon A-based contact lens with new UV-blocker (worn with spectacle frame without lenses)	ACUVUE® OASYS® Brand Contact Lenses with HYDRACLEAR® PLUS (worn with spectacle frame without lenses)	ACUVUE® OASYS® Brand Contact Lenses with HYDRACLEAR® PLUS worn Transitions® XTRActive™ – Gray Spectacles
Manufacturer	JJVC	JJVC	JJVC / TOI

	Test	Control 1	Control 2
Compass Protocol(s) and/or Lot Number or Other Identifier	██████████	Commercial ACUVUE OASYS	Commercial ACUVUE OASYS and plano Transitions spectacles
Lens Material	Senofilcon A	Senofilcon A	Senofilcon A XTRActive
Nominal Base Curve @ 22 °C	8.4	8.4	8.4
Nominal Diameter @ 22 °C	14.0	14.0	14.0
Nominal Distance Powers (D)	-1.00 through -6.00	-1.00 through -6.00	-1.00 through -6.00
Oxygen Permeability (Dk)	~ 103	~ 103	~ 103
Modality in Current Study	Daily wear	Daily wear	Daily wear
Replacement Frequency	Single use	Single use	Single use
Packaging Form (vial, blister, etc.)	Blister	Blister	Blister
Other distinguishing items	NA	NA	See spectacle table below

Approximately 30 Test lenses per sku will be needed for Visits 1, 2, 3 and 4. Since OASYS will be worn twice at each of these visits, approximately 60 control lenses per sku will be needed. Additional lenses may be shipped to cover any lenses lost, damaged, or heavy concentration on a particular power.

Examples of the spectacle frames are shown. The polycarbonate lenses will be 0.00 D in power and will contain the XTRActive photochromic agent from Transitions Optical Inc. The lenses will not contain an anti-reflective coating for a more valid comparison to the contact lenses. Half of the frames will have no lenses whatsoever and will be worn during the Test and OASYS trials to keep frame awareness the same as during the OASYS + photochromic spectacle trial.

Small unisex frames	Medium unisex frames	Large unisex frames

 • 2 with 0.00 D XTRActive lenses • 2 with no lenses 	
 • 2 with 0.00 D XTRActive lenses • 2 with no lenses 	
 • 2 with 0.00 D XTRActive lenses • 2 with no lenses
		

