3.13.	Lens Removal	The study lenses will be removed and discarded. A fresh pair of lenses will be used for each trial.	
3.14.	Test Treatments 2 and 3	Repeat steps 3.6 to 3.13 for the other testing treatments until all three have been completed.	

Visit 3: Closed-circuit on-road driving performance 1 (Day/night condition based on randomization)			
Step	Procedure	Details	
3.15.	Exit Slit Lamp Findings	
FDA Slit Lamp Classification Scale will be used to grade the findings.
 
If any of these slit lamp findings are grade 3 or higher, the subject is classified as having an adverse event. Adverse events shall be documented and followed until resolved, at which time they will be terminated from the study.
 
If the clearance of the fluorescein needs to be expedited, preservative-free rewetting drops or saline may be instilled.
	
3.16.	Exit Visual Acuity	
Record the distance logMAR visual acuity (OD, OS, and OU) to the nearest letter with their habitual correction in place. Subjects must read the smallest line until at least 50% of the letters are read incorrectly.
 
EDC: record logMAR acuity
	

VISIT 4

Visit 4: Closed-circuit on-road driving performance 2 (Day/night condition based on randomization)			
Step	Procedure	Details	
4.1.	As per Visit 3	Visit 4 follows the same procedures outlined in Visit 3, but is conducted under the opposite condition to Visit 3 (day/night).	

FINAL EVALUATION

The final evaluation will ordinarily take place immediately following the last scheduled follow-up visit per the study protocol. It may also take place at any point the subject discontinues the study or is terminated from the study.

Final Evaluation			
Step	Procedure	Details	
F.1	Final Exam Form	Indicate if the subject completed the study successfully. If subject discontinued from the study indicate the reason.	
F.2	Exit Visual Acuity	Record the distance logMAR visual acuity (OD, OS, and OU) to the nearest letter with their habitual correction in place. Subjects must read the smallest line until at least 50% of the letters are read incorrectly. EDC: record logMAR acuity	

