8.3. Entrance and Exit Visual Acuity (LogMAR)

Recorded visual acuity at the entrance and exit of each visit including unscheduled visits will be tabulated at eye level and subject level.

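### Step U.6 takes exit acuity at unscheduled visits through study spectacles that carry no refractive power, so the value is not comparable with the other exit acuities in the safety table

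*Protocol*

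**What the plan says.** Protocol section 7.3 lists six steps for an unscheduled visit. Entrance acuity (U.3) is recorded without naming any correction. U.4 is a bare-eye refraction with best corrected distance acuity for each eye and both eyes. U.5 is a slit lamp examination, after which the eyes may be rinsed with saline. U.6 then takes exit acuity "with the subjects wearing the study provided spectacle glasses".

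Section 6.1 describes what those spectacles are. Of the frames that carry lenses it says: "The polycarbonate lenses will be 0.00 D in power and will contain the XTRActive photochromic agent". Of the others: "Half of the frames will have no lenses whatsoever and will be worn during the Test and OASYS trials". Inclusion criterion 5 (section 3.2) says of each subject that the "spherical equivalent distance refraction must be in the range of -1.00 through -6.00 D (inclusive) in each eye".

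The exit acuities elsewhere in section 7.2 (steps 1.31, 2.15 and 3.16, and step F.2 of the Final Evaluation) are taken "with their habitual correction in place". Visit 4 repeats the Visit 3 procedures and so inherits this.

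SAP section 8.3, under the safety endpoints, states: "Recorded visual acuity at the entrance and exit of each visit including unscheduled visits will be tabulated". This is done by eye and by subject.

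**The concern.** U.6 names a correction that does not correct. The study spectacles exist to standardise frame wear and to deliver the photochromic filter over contact lenses; they were never meant to replace a subject's prescription. A site that follows U.6 as written, after the bare-eye steps before it, records a myope's unaided acuity, possibly through a photochromic lens. That number then goes into a planned safety tabulation alongside exit values taken in habitual correction.

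Unscheduled visits include those prompted by an ocular complaint, so a value that looks like an acuity loss only because the correction is missing is unhelpful there. A site that notices the problem has to choose its own correction. Different sites of judgement within one clinic could then produce inconsistent values or a protocol deviation. Because U.3 is silent on correction, the entrance-to-exit change within the same visit is also undefined.

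**Working it through.** The plan gives no figure to reproduce here. The check is a cross-reading of the sections with one subtraction.

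**Inputs**

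| Item | Value | Source |
|---|---|---|
| Correction at U.6 | Study spectacles; contact lenses not mentioned | Protocol 7.3 |
| Power of the spectacles with lenses | 0.00 D | Protocol 6.1 |
| Remaining frames | No lenses | Protocol 6.1 and synopsis |
| Eligible refraction | -1.00 to -6.00 D in each eye | Protocol 3.2, item 5 |
| Lens status before U.6 | Bare eye at U.4; no reinsertion described | Protocol 7.3 |
| Correction at other exit acuities | Habitual | Protocol 7.2, steps 1.31, 2.15, 3.16, F.2 |
| Use of the value | Safety tabulation | SAP 8.3 |

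**Step 1: are there any prescription study spectacles?** The frame table in section 6.1 lists three sizes, each with 2 plano-lensed and 2 lens-less frames: 3 × 2 = 6 plano and 3 × 2 = 6 lens-less, 12 in all. That is a shared stock for about 28 subjects, not individual prescriptions. The synopsis names only saline as an ancillary supply, and section 6.2 adds rewetting drops. No powered spectacles appear in either place.

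**Step 2: residual error.** With no contact lens in the eye, residual error = subject's refraction − spectacle power.

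- Least myopic eligible eye: -1.00 − 0.00 = -1.00 D.
- Most myopic eligible eye: -6.00 − 0.00 = -6.00 D.
- A lens-less frame also contributes 0.00 D, so the results are the same.

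None of the myopia is corrected, and since the range stops at -1.00 D, this applies to every eligible eye.

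**Step 3: comparability.** U.6 is the only exit acuity in the protocol not taken in habitual correction, and no reason is given for the difference. SAP 8.3 sets no separate rule for it.

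**Step 4: how far the effect reaches.**

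- U.4 records best corrected acuity at the same visit.
- Section 13.1 defines its acuity-loss criteria on best spectacle corrected acuity, not on exit acuity.
- Section 13.3 asks for best corrected acuity when an adverse event is found and when it ends. Section 8.2 asks for refraction with best corrected acuity on discontinuation.
- SAP section 2 summarises unscheduled visits separately and keeps them out of the primary and secondary analyses.
- SAP 8.3 only tabulates; no test or decision rule uses the value.

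**The case against.** The strongest objection is that U.6 does not say contact lenses are out. The only use the protocol describes for these frames is over contact lenses, and in that state vision would be corrected. The missing reinsertion step is not conclusive either, because steps 1.31, 2.15 and 3.16 also follow lens removal without one. This stands in part: uncorrected acuity is what the literal sequence gives, not something the text states outright. But those three steps name a correction that works by itself, whereas U.6 names only the spectacles. If lenses were intended underneath, U.6 would still have to say which lenses and which frame.

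The second objection, that the consequence is small, stands in full. Several stronger inferences are tempting and should not be drawn:

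- **A real loss of vision would be hidden.** A reader might conclude that true loss and missing correction could not be separated. U.4 separates them, because it gives best corrected acuity at the same visit.
- **The artefact could trigger or mask an adverse event classification.** The 2-line criteria in section 13.1 concern best spectacle corrected acuity, so a U.6 value neither meets nor conceals them.
- **The artefact amounts to a certain number of chart lines.** The documents support only the dioptric residual. They contain nothing that converts it to logMAR.
- **Efficacy conclusions are at risk.** They are not, since unscheduled visits are excluded from those analyses.

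Finally, nothing suggests that plano spectacles were chosen deliberately for this measurement. It is best read as a wording inconsistency.

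**Conclusion.** The point holds in a limited form. As written, U.6 conflicts with section 6.1, with inclusion criterion 5 and with every other exit-acuity step. Followed in sequence, it leaves -1.00 to -6.00 D uncorrected. This rests on one assumption: that contact lenses stay out after the bare-eye refraction at U.4, which the text implies but does not state. If lenses were worn, the fault would be an undefined correction rather than an absent one, and the step would still need rewording.

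The damage is confined to the unscheduled-visit exit values in the SAP 8.3 safety table, and to the entrance-to-exit comparison at those visits. Within that scope the literal rule affects every such record, but the documents give no expected number of unscheduled visits and there may be few or none. Detection of real loss, adverse event classification and the primary and secondary analyses are not affected. The correction is worth making because a stated measurement rule yields a non-comparable safety value and is easily put right.

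**What to change.** Reconcile U.6 with section 6.1 and with steps 1.31, 2.15, 3.16 and F.2 by recording unscheduled-visit exit acuity "with their habitual correction in place". Name the same correction at U.3, so that entrance and exit values at the visit can be compared.

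Habitual correction alone is not quite specific enough. Inclusion criterion 8 makes every subject a habitual soft contact lens wearer, while step 3.2 assumes that subjects also have habitual spectacles. U.3 and U.6 should therefore say whether the acuity is taken in spectacles or contact lenses, or require the site to record which was worn.

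The cost is a line of protocol wording at each of two steps, plus a data field if the correction worn is to be recorded. No new procedure is needed and the SAP 8.3 tabulation can stay as it is. If any unscheduled visit has already taken place under the present wording, the correction actually worn should be footnoted in that table.
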